8.3.2. Summary of Pharmacokinetic Parameters

- For each of these parameters, except for tmax, the following summary statistics will be calculated for each treatment:
 - o Non-transformed: median, maximum, minimum, arithmetic mean, 95% confidence interval for the arithmetic mean and standard deviation
 - Loge-transformed: geometric mean, 95% confidence interval for the geometric mean, standard deviation of logarithmically transformed data and between geometric coefficient of variation (CVb (%))
- For tmax, median, maximum, minimum, arithmetic mean, standard deviation and 95% Confidence Interval (CI) for the arithmetic mean will be calculated.
- An exploratory analysis will be performed using PK parameter plots in order to assess the results in Japanese and Caucasian subjects. Plots of AUC(0-t), AUC(0-inf), Cmax and T1/2 versus group (Japanese, Caucasian) will be produced.

10. APPENDICES

Section	Appendix
RAP Section 4	: Analysis Populations
Section 10.1	Appendix 1: Protocol Deviation Management
RAP Section 5	: General Considerations for Data Analyses & Data Handling Conventions
Section 10.2	Appendix 2: Time and Events
Section 10.3	Appendix 3: Treatment States & Phases
Section 10.4	Appendix 4: Data Display Standards & Handling Conventions
	Study Treatment & Sub-group Display Descriptors
	Baseline Definitions & Derivations
	Reporting Process & Standards
Section 10.5	Appendix 5: Derived and Transformed Data
	General
	Study Population
	Safety
	Pharmacokinetic
Section 10.6	Appendix 6: Premature Withdrawals & Handling of Missing Data
	General
	Study Population & Safety
Section 10.7	Appendix 7: Values of Potential Clinical Importance
	Laboratory Values
	• ECG
	Vital Signs
Other RAP App	endices
Section 10.8	Appendix 8: Abbreviations & Trade Marks
Section 10.9	Appendix 9: List of Data Displays
Section 10.10	Appendix 10: Example Mock Shells for Data Displays

10.1. Appendix 1: Protocol Deviation Management

Details will be referred latest Protocol Deviation Management Plan and data handling will be decided prior to final data base release.

10.2. Appendix 2: Time & Events

10.2.1. Protocol Defined Time & Event

	Scr	Day -1				Day 1				Day 2	Day 3	Day 4	Day 5	Day 6	Day 7	Day 8	Day 15 ⁴	Follow- up Day 22 ⁴
		-'	Pre	0 h	1 h	2 h	4 h	6 h	12 h	24 h	48 h	72 h	96 h	120 h	144 h	168 h	336 h	504 h
Admission to Unit		Χ																
Informed consent	Х																	
Subject demography/Medical history	Х																	
Physical examination	Х	Χ								Х	Χ	Χ	Χ	Χ	Χ	Χ		Χ
12-lead ECG	Х		Χ				Χ		Х	Х	Χ							Χ
Vital signs	Х		Χ				Х		Х	Х	Х	Х	Х	Х	Χ	Χ	Χ	Χ
Urine drug screen	Х	Χ																
Alcohol breath test	Х	Χ																
CO breath test	Х	Χ																
Serological test	Х																	
Haematology, clinical chemistry and urinalysis	Х	Х								Х			Х			Χ	Х	Х
Study treatment dosing				Х														
Calcium folinate dosing				X 1						Х	Х	Х	Х	Х	Χ	Χ		
PK Sampling			Χ		Х	Х	Х	Х	Х	Х	Х	Х		Х		Χ	Χ	Χ
SAEs ²	←== :	=====	=====	=====		=====			=====		=====		=====			=====	=====	÷=====
AEs ³				←===		=====												====→
Con Med review	←== :	=====	=====	======		=====			=====				=====				=====	====>
Discharge																Χ		
Outpatient Visit	Х																Χ	Χ

CONFIDENTIAL

204678

- Calcium folinate will be coadministered with Pyrimethamine on Day 1.
 All SAEs will be collected from the signing of the ICF until the follow-up visit at the time points specified.
- All AEs will be collected from the start of treatment until the follow-up visit at the time points specified.
 Subjects will return to the unit on Day 15 (±1) and 22 (±1) for the remaining PK samples and safety assessments post dose.

10.3. Appendix 3: Treatment States and Phases

10.3.1. Treatment Phases

Assessments and events will be classified according to the time of occurrence relative to the assessment date.

10.3.1.1. Treatment States for AE Data

Treatment State	Definition
Pre-Treatment	AE Start Date < Study Treatment Start Date and Time
On treatment	Dosing Start Date and Time in each group ≤ AE Start Date and Time
Onset Time Since	If Dosing Start Date and Time > AE Onset Date and Time = AE Onset Date and Time – Dosing Start Date and Time
First Dose (Minute)	If dosing Start Date and Time ≤ AE Onset Date and Time = AE Onset Date and Time - Dosing Start Date and Time +1 Missing otherwise
Onset Time Since Last Dose (Minute)	AE Start Date and Time – Most Recent Treatment Start Date and Time + 1
Duration (Minute)	AE Resolution Date and Time – AE Onset Date and Time + 1
Drug-related	If relationship is marked 'YES' on eCRF

10.4. Appendix 4: Data Display Standards & Handling Conventions

10.4.1. Study Treatment & Sub-group Display Descriptors

Treatment Group Descriptions									
RandAll NG Data Displays for Reporting									
Schedule	Description	Description	Order [1]						
1	D	Caucasian	2						
2	D	Japanese	1						

NOTES:

10.4.2. Baseline Definition & Derivations

10.4.2.1. Baseline Definitions

Parameter	Study Assessments Considered As Baseline			Baseline Used in
Faiailletei	Screening	Day -1	Day 1 (Pre-Dose)	Data Display
Safety				
12 Lead ECG & Vital Signs	Х		Х	Day 1 (Pre Dose)
Haematology	Х	Х		Day -1
Clinical Chemistry	X	Χ		Day -1

10.4.2.2. Derivations and Handling of Missing Baseline Data

Definition	Reporting Details
Change from Baseline	= Post-Dose Visit Value – Baseline

NOTES:

- Unless otherwise specified, the baseline definitions specified in Section 10.4.2.1 Baseline Definitions will be used for derivations for endpoints / parameters and indicated on summaries and listings.
- Unless otherwise stated, if baseline data is missing no derivation will be performed and will be set to missing.

10.4.3. Reporting Process & Standards

Reporting Area		
Software		
The currently supported versions of SAS software will be used.		
Reporting Area		
HARP Server	N/A	

^{1.} Order represents treatments being presented in TFL, as appropriate.

Reporting Area	
HARP Area	N/A
QC Spreadsheet	N/A

Analysis Datasets

 Analysis datasets will be created according to CDISC standards (SDTM IG Version 3.1.3 & AdaM IG Version 1.0).

Generation of RTF Files

N/A

Reporting Standards

General

- The current GSK Integrated Data Standards Library (IDSL) will be applied for reporting, unless otherwise stated:
 - 4.03 to 4.23: General Principles
 - 5.01 to 5.08: Principles Related to Data Listings
 - 6.01 to 6.11: Principles Related to Summary Tables
 - 7.01 to 7.13: Principles Related to Graphics

Formats

- All data will be reported according to the actual treatment the subject received unless otherwise stated.
- GSK IDSL Statistical Principles (4.24) for decimal places (DP's) will be adopted for reporting of data based on the raw data collected.
- Numeric data will be reported at the precision collected on the eCRF.
 - The reported precision from non eCRF sources will follow the IDSL statistical principles but may be adjusted to a clinically interpretable number of DP's.

Planned and Actual Time

- Reporting for tables, figures and formal statistical analyses :
 - Planned time relative to dosing will be used in figures, summaries, statistical analyses and calculation of any derived parameters, unless otherwise stated..
 - For PK parameters derivation, actual times are used.
 - The impact of any major deviation from the planned assessment times and/or scheduled visit days on the analyses and interpretation of the results will be assessed as appropriate.
- Reporting for Data Listings:
 - Planned and actual time relative to study drug dosing will be shown in listings (Refer to IDSL Statistical Principle 5.05.1).
 - Unscheduled or unplanned readings will be presented within the subject's listings.
 - Visits outside the protocol defined time-windows (i.e. recorded as protocol deviations) will be included in listings but omitted from figures, summaries and statistical analyses.

Unscheduled Visits

- Unscheduled visits will not be included in summary tables.
- Unscheduled visits will not be included in figures.

Reporting Standard	s		
All unscheduled visits will be included in listings.			
Descriptive Summa	ry Statistics		
Continuous Data	Refer to IDSL Statistical Principle 6.06.1		
Categorical Data	N, n, frequency, %		
Reporting of Pharm	acokinetic Concentration Data		
Descriptive	Refer to IDSL Statistical Principle 6.06.1		
Summary Statistics	Assign zero to NQ values (Refer to GUI_51487 for further details)		
Reporting of Pharm	acokinetic Parameters		
Descriptive Summary Statistics (Log Transformed)	N, n, geometric mean, 95% CI of geometric mean, standard deviation (SD) of logged data and between geometric coefficient of variation (CVb (%)) will be reported. $ \text{CV}_b \text{ (\%)} = \sqrt{\left(\text{exp}(\text{SD}^2) - 1\right) * 100} $ (SD = SD of log transformed data)		
Parameters Not Being Log Transformed	Tmax		
Parameters Not Being Summarised	The following PK parameters will not be summarised but listed: %AUCex, Tlast, lambda_z, lambda_z_lower, lambda_z_upper, #pts, R2		
Graphical Displays			
Refer to IDSL Statistical Principals 7.01 to 7.13.			

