10.5. Appendix 5: Derived and Transformed Data

10.5.1. General

Multiple Measurements at One Time Point

- Mean of the measurements will be calculated and used in any derivation of summary statistics but if listed, all data will be presented.
- If there are two values within a time window the value closest to the target day for that window will be used. If values are the same distance from the target then the mean will be taken.
- Subjects having both High and Low values for Normal Ranges at any post-baseline visits for safety parameters will be counted in both the High and Low categories of "Any visit postbaseline" row of related summary tables. This will also be applicable to relevant Potential Clinical Importance summary tables.

Study Day

- Calculated as the number of days from study day of start of dosing date :
 - Ref Date = Missing
- → Study Day = Missing
- Ref Date < Dosing Start Date → Study Day = Ref Date Dosing Start Date
- Ref Data ≥ Dosing Start Date → Study Day = Ref Date (Dosing Start Date) + 1

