10.9.5. Safety Tables

Safety	: Tables				
No.	Population	IDSL / TST ID / Example Shell	Title	Programming Notes	Deliverable [Priority]
Advers	e Events (AEs)				
2.1.	Safety	AE1	Summary of All Adverse Events by System Organ Class and Preferred Term		SAC [1]
2.2.	Safety	AE5A	Summary of All Adverse Events by Maximum Intensity		SAC [1]
2.3.	Safety	AE1	Summary of All Drug-Related Adverse Events by System Organ Class and Preferred Term		SAC [1]
2.4.	Safety	AE5A	Summary of All Drug-Related Adverse Events by Maximum Intensity		SAC [1]
Labora	tory: Chemistry	y			
2.5.	Safety	LB1	Summary of Chemistry		SAC [1]
2.6.	Safety	LB1	Summary of Chemistry Changes from Baseline		SAC [1]
2.7.	Safety	LB4	Summary of Chemistry Data Shifts from Baseline with Respect to the Normal Range		SAC [1]
Labora	tory: Hematolo	gy			
2.8.	Safety	LB1	Summary of Hematology		SAC [1]
2.9.	Safety	LB1	Summary of Hematology Changes from Baseline		SAC [1]
2.10.	Safety	LB4	Summary of Hematology Data Shifts from Baseline with Respect to the Normal Range		SAC [1]

Safety	Safety : Tables					
No.	Population	IDSL / TST ID / Example Shell	Title	Programming Notes	Deliverable [Priority]	
Labora	tory: Urinalysis	,			-	
2.11.	Safety	UR3b	Summary of Urinalysis (Glucose, Protein, Blood, Ketones, Bilirubin, Urobilinogen nitrite, leukocyte esterase) Data		SAC [1]	
2.12.	Safety	LB1	Summary of Urinalysis (Specific Gravity and pH)		SAC [1]	
ECG						
2.13.	Safety	EG1	Summary of ECG Findings		SAC [1]	
2.14.	Safety	EG2	Summary of ECG Value		SAC [1]	
2.15.	Safety	EG2	Summary of Change from Baseline in ECG Values by Visit		SAC [1]	
Vital Si	Vital Signs					
2.16.	Safety	VS1	Summary of Vital Signs		SAC [1]	
2.17.	Safety	VS1	Summary of Change from Baseline in Vital Signs		SAC [1]	

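### Minor: SAP 10.4.3 makes no exception for the any-visit post-baseline High/Low row, so as written the row omits a value seen only at an unscheduled or out-of-window draw

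*SAP*

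**What the plan says.** SAP 10.4.3 sets two general rules for what enters summary displays. For unscheduled visits: "Unscheduled visits will not be included in summary tables". For visits off schedule: "Visits outside the protocol defined time-windows (i.e. recorded as protocol deviations) will be included in listings but omitted from figures, summaries". Both kinds of visit remain in listings. The only post-dose visits with a stated window are Day 15 and Day 22, each plus or minus one day (Protocol section 2; SAP 10.2.1).

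SAP 10.5.1 then describes the row at issue. "Subjects having both High and Low values for Normal Ranges at any post-baseline visits" are to be counted under both headings in the any-visit post-baseline row of the related summary tables. It adds: "This will also be applicable to relevant Potential Clinical Importance summary tables". The same section has two rules for more than one measurement: "Mean of the measurements will be calculated and used in any derivation of summary statistics", and "If there are two values within a time window the value closest to the target day for that window will be used".

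SAP 10.9.5 lists the tables where such a row would naturally sit: Table 2.10, "Summary of Hematology Data Shifts from Baseline with Respect to the Normal Range", and its chemistry counterpart, Table 2.7. Both cite shell LB4, which is not reproduced.

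**The concern.** A row labelled as covering any post-baseline visit is normally read as a worst-case count: did this subject ever leave the normal range after dosing? SAP 10.4.3 limits the row to scheduled, in-window visits, and its label does not tell the reader so.

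The excluded draws are not arbitrary. Protocol section 9 allows repeat or unscheduled samples for safety reasons, and Protocol 9.3.4 calls for clinically significant abnormal results to be repeated. Draws prompted by a safety question are among those most likely to be informative. Haematological toxicity is a named risk in Protocol 3.3.1, and laboratory change is part of a secondary endpoint.

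The row is also the only worst-case laboratory count that the SAP text describes. SAP 10.5.1 mentions summary tables of potential clinical importance, but none of Tables 2.1 to 2.17 is one.

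**Working it through.** The plan states no figure to reproduce, so the check traces each kind of post-dose value through the rules.

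**Inputs**
- Exclusion rules: SAP 10.4.3.
- Row description, mean rule and closest-value rule: SAP 10.5.1.
- Baseline for haematology and chemistry: Day -1 (SAP 10.4.2.1).
- Windows: Day 15 ± 1 covers Days 14–16; Day 22 ± 1 covers Days 21–23.
- Group size: 6 (SAP 2.3).

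**Tracing a High or Low value to the any-visit row**
1. Scheduled, in-window draw with no repeat: counted, as it should be.
2. Seen only at an unscheduled visit: removed by SAP 10.4.3, so not counted.
3. Seen only at a Day 15 or Day 22 visit held outside its window, for example on Day 17: omitted from summaries by SAP 10.4.3, so not counted.
4. Abnormal at a scheduled draw, with a later repeat classed as unscheduled: the scheduled value counts and the repeat is excluded. Nothing is lost.
5. Repeat treated as the same time point: the mean rule may apply. With illustrative values, ALT 1.2 × ULN and a repeat of 0.7 × ULN give (1.2 + 0.7)/2 = 0.95 × ULN, which is not High. This matters only if the High/Low flag is set on the mean, and the SAP does not say that it is.
6. Two values in one window: the one nearer the target day is kept. If the other was the abnormal one, it may be dropped.

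Routes 2 and 3 follow directly from the text. Routes 5 and 6 depend on how a repeat is classified and on how flags are derived.

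**Search for an exception.** Neither document has one. SAP 10.6.1, on withdrawn subjects, admits available planned data to summary tables, which points the same way as SAP 10.4.3. SAP 10.4.3 also says that "The impact of any major deviation from the planned assessment times and/or scheduled visit days" will be assessed as appropriate, and SAP 10.1 leaves deviation handling to a decision before database release. Neither makes an exception for this row.

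**Size.** One omitted subject changes a group's row from 1/6 = 16.7% to 0/6 = 0%, a difference of 16.7 percentage points.

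**Can other outputs replace the row?** Only in part. Listings 20 and 22 hold all chemistry and haematology values. Listings 21 and 23 select subjects on the thresholds in SAP 10.7.1, not on the normal range. For ALT the threshold is 2 × ULN or more, so a lone value of 1.2 × ULN is High but would not by itself place the subject in Listing 21.

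**The case against.** The strongest reply is that the plan already has a rule. SAP 10.4.3 is general, the row sits in a summary table, and so the row is scheduled-only by convention. On that view the point is a preference for worst-case counting. This stands in part: the SAP is not silent. But the stated rule suits by-visit rows better than a row whose label promises any visit, and the wording of SAP 10.5.1 can be read more widely than SAP 10.4.3 allows.

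A second reply is that the shell and the sponsor's display standards are not available and may settle the matter. That is fair, and placing the row in Tables 2.7 and 2.10 remains an inference. However, SAP 10.4.3 applies those standards unless otherwise stated, and the same section does state otherwise.

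A third reply is that little turns on it, and this stands. Adverse events and change from baseline have their own tables, there is no hypothesis test, and with about 12 subjects the listings can be read in full. Repeats under Protocol 9.3.4 follow an abnormal value, which is usually already counted if that draw was scheduled.

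A reader might infer that the multiple-measurement rules can only hide shifts and never create one. The documents do not support that. Tables 2.7 and 2.10 show shifts from baseline, and the mean rule is not limited to post-dose values. Day -1 ALT values of 1.2 and 0.7 × ULN average 0.95 × ULN, a normal baseline; a later 1.1 × ULN is then a shift to High, although one pre-dose value was already High.

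**Conclusion.** The point holds as a minor, cheap improvement. As written, the any-visit post-baseline row omits a High or Low value seen only at an unscheduled post-dose draw, or only at a Day 15 or Day 22 visit outside ± 1 day. That undercounts worst-case laboratory shifts by one subject in six for each subject affected.

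This rests on two assumptions: that the row appears in Tables 2.7 and 2.10, and that SAP 10.4.3 governs it.

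Two wider readings should not be drawn. A reader might infer that much of the laboratory data is at risk because two scheduled post-dose draws carry a window. Having a window is not the same as missing it, and the documents give no rate for unscheduled or out-of-window draws. A reader might also infer that averaging will certainly mask abnormal repeats. The mean rule speaks of summary statistics at one time point, and the SAP does not say that High/Low flags use the mean, so that route is only possible.

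No data are lost and no pharmacokinetic result is affected. Clinically relevant laboratory changes are still recorded as adverse events.

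**What to change.** Keep by-visit rows on scheduled, in-window data. Add one sentence to SAP 10.4.3 or 10.5.1: any-visit post-baseline rows use every valid individual post-dose value, whether scheduled, unscheduled, repeat or out-of-window, excluding technically invalid samples, with baseline as defined in SAP 10.4.2.1.

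Add a footnote to the tables that carry the row, saying two things: the count depends partly on how often a subject is tested, and individual post-dose values are compared with a single baseline that may itself be an average.

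If the sponsor prefers to keep the row scheduled-only, a footnote saying so would stop the label from misleading.

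The cost is one sentence, one footnote and a small programming change before database release. The trade-off is that a subject tested more often has more chances to show a shift, and that a worst individual value is set against one baseline. The footnote discloses both.

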10.5. Appendix 5: Derived and Transformed Data

10.5.1. General

Multiple Measurements at One Time Point

- Mean of the measurements will be calculated and used in any derivation of summary statistics but if listed, all data will be presented.
- If there are two values within a time window the value closest to the target day for that window will be used. If values are the same distance from the target then the mean will be taken.
- Subjects having both High and Low values for Normal Ranges at any post-baseline visits for safety parameters will be counted in both the High and Low categories of "Any visit postbaseline" row of related summary tables. This will also be applicable to relevant Potential Clinical Importance summary tables.

Study Day

- Calculated as the number of days from study day of start of dosing date :
 - Ref Date = Missing
- → Study Day = Missing
- Ref Date < Dosing Start Date → Study Day = Ref Date Dosing Start Date
- Ref Data ≥ Dosing Start Date → Study Day = Ref Date (Dosing Start Date) + 1

10.5.2. Study Population

Demographics

Age

- GSK standard IDSL algorithms will be used for calculating age where birth date will be imputed as:
 - Any subject with a missing day will have this imputed as day '15'.
 - Any subject with a missing date and month will have this imputed as '30th June'.
- Birth date will be presented in listings as 'YYYY'.
- Reference date for calculation of age at screening will be from visit 1 (Screening visit) date, however this will be from screen failure date for a screen failure subject.
- Analysis age group will be categorized (Years):
 - <=18, 19-64, 65-74, >=75
- Age will be categorized for EudraCT: Adults (18-64 years)

Body Mass Index (BMI)

• Calculated as Weight (kg) / [Height (m)²

10.5.3. Safety

ECG Parameters

RR Interval

IF RR interval (msec) is not provided directly, then RR can be derived as :

[1] If QTcB is machine read & QTcF is not provided, then:

$$RR = \left[\left(\frac{QT}{QTcB} \right)^2 \right] * 1000$$

[2] If QTcF is machine read and QTcB is not provided, then:

$$RR = \left[\left(\frac{QT}{QTeF} \right)^3 \right] * 1000$$

• If ECGs are manually read, the RR value preceding the measurement QT interval should be a collected value THEN do not derive.

Corrected QT Intervals

 When not entered directly in the eCRF, corrected QT intervals by Bazett's (QTcB) and Fredericia's (QTcF) formulas will be calculated, in msec, depending on the availability of other measurements.

IF RR interval (msec) is provided then missing QTcB and/or QTcF will be derived as :

$$QTcB = \frac{QT}{\sqrt{\frac{RR}{1000}}}$$

$$QTcF = \frac{QT}{3\sqrt{\frac{RR}{1000}}}$$

Laboratory Parameters

• If a laboratory value which is expected to have a numeric value for summary purposes, has a non-detectable level reported in the database, where the numeric value is missing, but typically a character value starting with '<x' or '>x' (or indicated as less than x or greater than x in the comment field) is present, the number of significant digits in the observed values will be used to determine how much to add or subtract in order to impute the corresponding numeric value.

 \circ Example 1: 2 Significant Digits = '< x ' becomes x – 0.01

○ Example 2: 1 Significant Digit = '> x' becomes x + 0.1

○ Example 3: 0 Significant Digits = '< x' becomes x – 1

Laboratory Assessments			
Haematology	Platelet Count, RBC Count, Haemoglobin, Hematocrit, RBC Indices (MCV, MCH, MCH, %Reticulocytes), WBC count with Differential (Neutrophils, Lymphocytes, Monocytes, Eosinophils, Basophils)		
Clinical Chemistry	BUN, Creatinine, Glucose (fasting), Potassium, Sodium, Calcium, Aspartate Aminotransferase (AST), Alanine Aminotransferase (ALT), Alkaline phosphatise, Total and direct bilirubin, Total Protein		
Routine Urinalysis	Specific gravity, pH (assessed by dipstick) • glucose, protein, blood, ketones, bilirubin, urobilinogen, nitrite, leukocyte esterase by dipstick		

Laboratory Assessments

Microscopic examination (if blood or protein is abnormal)

ECG (12-lead ECG)

ECG findings, ECG values (Heart rate, PR interval, QRS duration, QT interval, and QTcF intervals)

Vital Signs

Pulse rate, Blood pressure (Systolic, Diastolic), respiratory rate, Temperature

